1.2.5 Study MTD Determination/Dose Expansion

Arm 1 (Amendment Version Date 4/13/2021)

At dose level 1, only mild radiation related AEs have occurred with no PSA recurrence of the as of yet. At dose level 2, 2 participants in arm 1 have had some significant urine toxicity (Grade 3 hematuria, transient and Grade 3 urinary incontinence) that do not meet the protocol endpoint for maximum tolerated dose (MTD).

Since no one has failed at dose level 1 and the toxicity was less significant, the protocol has been amended to change the criteria for late DLT to Grade 3 urinary toxicity (instead of Grade 4), which would allow us to consider dose level 1 as MTD in Arm 1, trigger expansion at that cohort, and halt dose escalation. These changes would reduce the risk to participants.

Arm 2 (Amendment Version Date 10/12/2021)

Determination has been made to expand dose level 2 for arm 2. Three patients have been treated at dose level 1 and three patients have been treated at dose level 2 (one is currently undergoing treatment). Toxicity has not exceeded grade 2 urinary or grade 3 bowel. Of all 5 patients in this arm who have completed treatment, there is no evidence of recurrence.

Based on recent accumulating literature from the definitive treatment setting (no prior radiation), it is clear that further escalation of dose may have long term toxicity. Thus, in the face of excellent disease control, we feel it would be inappropriate to increase dose further as it will expose patients to risk without additional benefit.

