|-------------------|---------------------------------|----------------------|--|----------------------|
| Dose level | Dose to prostate | Dose to tumor | Dose to prostate | Dose to tumor |
| Level 1 | - | 40 Gy | 30 Gy | 40 Gy |
| Level 2 | - | 42.5 Gy | 30 Gy | 42.5 Gy |
| Level 3* | | 45 Gy | 30 Gy | 45 Gy |

* As of amendment version dates 4/13/2021 and 10/12/2021, determination has been made not to escalate to dose level 3 for both arms. Refer to section [1.2.5](#).

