3.1.1 Dose Limiting Toxicity

Dose-limiting toxicities will be defined as follows (during treatment and within the first three weeks after treatment):

- Grade 3 rectal, small bowel, or urinary toxicity that does not resolve to Grade 2 or less within 4 days with appropriate medical management
- Other grade 3 in-field toxicities attributable to SBRT that do not resolve to Grade 2 or less within 4 days with appropriate medical management
- Delays of more than one week in completing radiation treatment due to toxicity (cumulative duration of delay over the course of the entire treatment).

Additionally, late toxicities (those that occur after 90 days following completion of treatment) will be followed and scored but will not be used for escalation with the following exception.

If Grade ≥ 4 late bowel or Grade ≥ 3 bladder injury is observed in 2 patients in any cohort, dose escalation will be terminated in that arm and the dose below that dose level in which the toxicity was observed will be considered the MTD. The criteria for late DLT for bladder were changed to Grade 3 to Grade 4 via amendment version date 04/13/2021, and should apply retroactively to all prior participants. MTD will be determined for each arm separately. Early and late toxicities used for assessment of DLTs should be attributable (possible, probable or definite) to SBRT. Changes in sexual and erectile function will not be considered a DLT.

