3.1.2 Dose Escalation

Dose escalation will proceed in parallel in Arm 1 (Tumor Irradiation) and Arm 2 (Prostate and Tumor Irradiation) in groups of 3–6 patients. The MTD is the dose level at which no more than 1 of up to 6 patients experience DLT during treatment and up to 3 weeks following completion of treatment, and the dose below that at which at least 2 (of ≤ 6) patients have DLT as a result of treatment. If a patient did not experience DLT and did not finish treatment, he will not be evaluable for toxicity and will be replaced in the dose level (See [Table 2](#)).

Dose escalation will follow the rules outlined in [Table 3](#) below for each Arm (1 or 2) independently as MTD and toxicities are expected to be different as a result of prior treatment.

Table 3: Escalation Decision Rule

| Number of Patients with DLT at a Given Dose Level | Escalation Decision Rule |
|---|--|
| 0 out of 3 | Enter up to 3 patients at the next dose level |
| ≥ 2 | Dose escalation will be stopped. This dose level will be declared the maximally administered dose (highest dose administered). Up to three (3) additional patients will be entered at the next lowest dose level if only 3 patients were treated previously at that dose. |
| 1 out of 3 | Enter up to 3 more patients at this dose level. 
• If 0 of these 3 patients experience DLT, proceed to the next dose level.• If 1 or more of this group suffer DLT, then dose escalation is stopped, and this dose is declared the maximally administered dose. Up to three (3) additional patients will be entered at the next lowest dose level if only 3 patients were treated previously at that dose. |
| ≤ 1 out of 6 at highest dose level below the maximally administered dose | This is the MTD and is generally the recommended phase 2 dose. 6 additional patients may be entered at the recommended phase 2 dose. |

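### The late-toxicity rule in 3.1.1 still speaks only of escalation: during expansion it triggers no accrual action, and at Arm 1 level 1 it names an MTD that Table 2 does not contain

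*Combined protocol and SAP*

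**What the plan says.** Section 3.1.1 scores late toxicities (more than 90 days after treatment) but keeps them out of escalation decisions, with one exception. If 2 patients in any cohort have late bowel injury of Grade 4 or more, or bladder injury of Grade 3 or more, "dose escalation will be terminated in that arm and the dose below that dose level in which the toxicity was observed" is taken as the MTD. No other consequence is given.

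The footnote to Table 2 (section 3.1) records that "determination has been made not to escalate to dose level 3 for both arms". Section 1.2.5 explains what remains. For Arm 1, the amendment of 4/13/2021 lowered the late urinary criterion from Grade 4 to Grade 3 so as to "consider dose level 1 as MTD in Arm 1, trigger expansion at that cohort, and halt dose escalation". For Arm 2, the amendment of 10/12/2021 says "Determination has been made to expand dose level 2 for arm 2". Table 3 (section 3.1.2) provides that "6 additional patients may be entered at the recommended phase 2 dose" and attaches no stopping rule to those patients.

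**The concern.** The rule has two effects: it ends escalation and it moves the MTD down one level. The first has nothing left to act on. The second depends on a lower level existing, and Arm 1 is expanding at the lowest level in Table 2. The MTD is the primary endpoint. Applied literally, two severe late injuries at Arm 1 level 1 would leave that endpoint without a dose, and in neither arm would the trigger itself stop further patients from being treated at the level concerned.

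Severe urinary toxicity has already occurred in this trial: section 1.2.5 reports that "2 participants in arm 1 have had some significant urine toxicity (Grade 3 hematuria, transient and Grade 3 urinary incontinence" at dose level 2. The current text does not say what would follow if qualifying late events occurred in expansion.

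**Working it through.** **Step 1. Apply the rule at each expansion level** (dose levels from Table 2).

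| Arm | Expansion level | Effect of ending escalation | Dose below | Accrual action stated |
|---|---|---|---|---|
| 1 | Level 1, 40 Gy | None, already closed | Not in Table 2 | None |
| 2 | Level 2, 42.5 Gy | None, already closed | Level 1, 40 Gy | None |

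The missing dose is therefore an Arm 1 problem. The missing accrual action affects both arms.

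**Step 2. See whether other sections supply the outcome.**

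- *3.1.2, MTD definition.* It counts DLTs only during treatment and up to 3 weeks afterwards. Late events begin after 90 days. So 3.1.2 could still name Arm 1 level 1 while 3.1.1 points below it, and nothing says which governs.
- *Table 3, row for two or more DLTs.* It says "Up to three (3) additional patients will be entered at the next lowest dose level", provided only 3 were treated there. This fits Arm 2, where section 1.2.5 reports "Three patients have been treated at dose level 1 and three patients have been treated at dose level 2", so level 1 could be filled from 3 to 6. It cannot be used at Arm 1 level 1. Section 3.1.1 does not refer to this row.
- *10.4.1.* A level with 2 unacceptable toxicities has exceeded the MTD. The text assumes groups of 3–6 and then takes the next lower level, so it gives half of the Arm 1 conclusion and stops short of the outcome.
- *7.4.1 and 12.1.* The team reviews patients weekly and bases dose-level enrollment on toxicity; the study may be suspended for unacceptable risk. Neither has a threshold or a link to the 3.1.1 trigger.

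**Step 3. Check the unit of the count.** Sections 2.3.1 and 3.1 define cohorts by prior treatment (EBRT or brachytherapy). Section 1.2.5 uses the word for a dose level. On the first meaning, late events at different levels of Arm 1 would be added together, and the level in which the toxicity was observed would no longer be unique.

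**Step 4. Chance that an automatic pause is triggered.** The plan gives no operating characteristics and no target late rate, so there is no figure to reproduce and every rate below is an assumption. Take n = 6 (Table 3's expansion size), with earlier patients at the level staying event-free:

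P(X ≥ 2) = 1 − (1−p)^6 − 6p(1−p)^5

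| Assumed rate p | (1−p)^6 | 6p(1−p)^5 | P(X ≥ 2) |
|---|---|---|---|
| 5% | 0.735 | 0.232 | 0.033 |
| 2/29 = 6.9% | 0.651 | 0.289 | 0.059 |
| 10% | 0.531 | 0.354 | 0.114 |
| 20% | 0.262 | 0.393 | 0.345 |

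The 2/29 is the Grade 3 or higher GU count in the SBRT series in section 1.2.1. That series treated the prostate gland to 34 Gy in 5 fractions, a different regimen, and its Grade 4 case is not labelled late.

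**The case against.** The strongest reply is that little is left uncovered. Section 10.4.1 already says that such a level exceeded the MTD, and that no tolerable dose was established is the usual inference when the lowest level fails. Weekly review under 7.4.1 covers enrollment as well as escalation, 12.1 allows suspension, and Table 3's expansion is permissive. In a single-institution Phase I trial, preferring team judgement to an automatic pause is defensible. This stands as a reason to rate the point low. It does not supply the Arm 1 outcome, settle the conflict between 3.1.1 and 3.1.2, or connect discretion to the protocol's own trigger. A reader might infer that patients in expansion have no protection, or that treatment must continue after two injuries; the documents do not support either.

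Two other inferences are tempting.

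- *That the 2021 amendment for Arm 1 settled the rule's consequence after the events.* Sections 1.2.5 and 3.1.1 describe a change in the grade that counts, not in what follows. The two reported events were at level 2, not the Arm 1 expansion dose, and 1.2.5 does not call them late. They are not an instance of the gap described here.
- *That the chance of meeting the rule at Arm 1 level 1 should be worked out over everyone ever treated there.* Section 1.2.5 reports only mild radiation-related events at that level, so patients already observed cannot be counted as if unobserved. New late events among them remain possible and would raise the Step 4 figures.

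**Conclusion.** The gap is real but minor. On the current text, meeting the late rule in expansion has no stated accrual consequence in either arm, and in Arm 1 it yields no usable MTD. In Arm 2 the MTD clause works. This rests on the wording alone and needs no assumed rate.

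The probabilities (3%, 6%, 11% and 34%) show how often the proposed pause might be triggered. They rest on assumed rates, 6 expansion patients and no events among earlier patients; they are higher if more patients at the level are still unobserved. They do not measure the safety benefit. Late events start after 90 days and may appear once accrual has ended, when a pause protects nobody, and the documents do not give accrual timing. Even then the MTD conclusion would still have to be stated, because follow-up runs to 24 months.

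**What to change.** Amend 3.1.1, with a cross-reference in 3.1.2, to state that:

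1. The count of 2 is kept and applies to all patients treated at a given dose level within an arm, including expansion patients. The amendment should say openly that this settles the ambiguous unit of the present rule.
2. Meeting the count suspends further accrual at that level pending review.
3. The late rule overrides the 3-week MTD definition in 3.1.2.
4. In Arm 2, level 1 becomes the candidate MTD and is filled to 6 under Table 3's row for two or more DLTs.
5. In Arm 1, level 1 exceeds the MTD and no tolerable dose was established.

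This takes a few sentences and no new data. The price is a possible pause at a dose that is in fact tolerable, with the chances in Step 4; these should be stated beside the rule with their assumptions.

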3.1.2 Dose Escalation

Dose escalation will proceed in parallel in Arm 1 (Tumor Irradiation) and Arm 2 (Prostate and Tumor Irradiation) in groups of 3–6 patients. The MTD is the dose level at which no more than 1 of up to 6 patients experience DLT during treatment and up to 3 weeks following completion of treatment, and the dose below that at which at least 2 (of ≤ 6) patients have DLT as a result of treatment. If a patient did not experience DLT and did not finish treatment, he will not be evaluable for toxicity and will be replaced in the dose level (See [Table 2](#)).

Dose escalation will follow the rules outlined in [Table 3](#) below for each Arm (1 or 2) independently as MTD and toxicities are expected to be different as a result of prior treatment.

Table 3: Escalation Decision Rule

| Number of Patients with DLT at a Given Dose Level | Escalation Decision Rule |
|---|--|
| 0 out of 3 | Enter up to 3 patients at the next dose level |
| ≥ 2 | Dose escalation will be stopped. This dose level will be declared the maximally administered dose (highest dose administered). Up to three (3) additional patients will be entered at the next lowest dose level if only 3 patients were treated previously at that dose. |
| 1 out of 3 | Enter up to 3 more patients at this dose level. 
• If 0 of these 3 patients experience DLT, proceed to the next dose level.• If 1 or more of this group suffer DLT, then dose escalation is stopped, and this dose is declared the maximally administered dose. Up to three (3) additional patients will be entered at the next lowest dose level if only 3 patients were treated previously at that dose. |
| ≤ 1 out of 6 at highest dose level below the maximally administered dose | This is the MTD and is generally the recommended phase 2 dose. 6 additional patients may be entered at the recommended phase 2 dose. |

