3.8.4 Treatment Delivery

An SBRT set up will be used for all treatments. Treatment will be delivered in 5 fractions over a span of 7-14 days. Image guidance will include pre-treatment cone beam CT as per standard of care. An additional post-treatment cone beam CT after each fraction will be obtained to assess intrafraction motion. Calypso beacons will be utilized for real time tumor tracking as per the standard of care if implanted.

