7.4 DATA AND SAFETY MONITORING PLAN

7.4.1 Principal Investigator/Research Team

The clinical research team will meet on a weekly basis when patients are being actively treated on the trial to discuss each patient. Decisions about dose level enrollment and dose escalation if applicable will be made based on the toxicity data from prior patients.

All data will be collected in a timely manner and reviewed by the principal investigator or a lead associate investigator. Events meeting requirements for expedited reporting as described in section [7.2.1](#) will be submitted within the appropriate timelines.

The principal investigator will review adverse event and response data on each patient to ensure safety and data accuracy. The principal investigator will personally conduct or supervise the investigation and provide appropriate delegation of responsibilities to other members of the research staff.

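### The replacement rule in 3.1.2 makes no exception for SBRT stopped because of toxicity below the DLT threshold, so such a patient can leave the MTD count

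*Combined protocol and SAP*

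**What the plan says.** All references are to the combined protocol and SAP.

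- **Replacement (3.1.2).** "If a patient did not experience DLT and did not finish treatment, he will not be evaluable for toxicity and will be replaced". No exception is made by reason for stopping.
- **Acute DLTs (3.1.1).** Two criteria need Grade 3 toxicity that has not come down to Grade 2 within 4 days. The third carries no grade: "Delays of more than one week in completing radiation treatment due to toxicity (cumulative duration of delay over the course of the entire treatment)". Attribution is broad: "Early and late toxicities used for assessment of DLTs should be attributable (possible, probable or definite) to SBRT". Sexual and erectile changes are excluded.
- **Leaving therapy (3.10.1).** Unacceptable toxicity is a ground, defined by reference to 3.1.1. Patient request and investigator discretion are separate grounds with no such link.
- **Schedule and dose (3.8.4, 3.3).** "Treatment will be delivered in 5 fractions over a span of 7-14 days". Radiation dose may not be modified.
- **Evaluability (6.3.1, 10.3).** Everyone who starts SBRT is evaluable for toxicity. Neither section mentions the 3.1.2 exclusion.
- **MTD test (3.1.2, 10.4.1).** At most 1 of 6 patients may have a DLT at the MTD.
- **Status (1.2.5, 3.1).** A footnote to Table 2 records that "determination has been made not to escalate to dose level 3 for both arms".

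**The concern.** The plan already treats toxicity that disrupts the course as dose-limiting: a patient who pauses for more than a week and then finishes is a DLT whatever the grade. A patient with the same toxicity who never finishes has no explicit status. If the delay criterion is taken to presuppose completion, he has no DLT, and 3.1.2 removes him from the count and brings in someone else. The more complete disruption then counts for less than the partial one.

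Because the dose cannot be reduced, a patient who tolerates treatment poorly can only continue, pause or stop, so stopping is a real option. The MTD is the primary endpoint, and with six patients at a level a single reclassified patient can change the answer.

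**Working it through.** **Which toxicity stops are affected**

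1. Grade 3 lasting beyond 4 days: a DLT under 3.1.1, finished or not. Not affected.
2. Removal for unacceptable toxicity under 3.10.1: a DLT by cross-reference. Not affected.
3. A stop by request or discretion, for attributable Grade 2 or lower toxicity or for Grade 3 that settles within 4 days: no graded criterion applies, so everything depends on the delay criterion.
   - Reading C: more than a week beyond the 7-14 day schedule he has still not completed because of toxicity, so he is a DLT.
   - Reading A: a delay in completing presupposes completion, so he has no DLT and is replaced.

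Sections 6.3.1 and 10.3 do not settle case 3. Even if they overrode 3.1.2, they would only keep him in the denominator. They do not make his stop a DLT.

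**Direction (no assumed rate needed)**

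Take a level of six with one DLT and one case-3 stop. Under C the count is 2/6, above the MTD. Under A it is 1/6, within the MTD, if the replacement has no DLT. If the replacement has one, it is 2/6 either way. A never gives a higher count than C.

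In general, let d be the DLT rate apart from such stops and s the rate of such stops. The counted event rate is p = d + s under C and p = d/(1 − s) under A. The difference, (d + s) − d/(1 − s), equals s(1 − d − s)/(1 − s). This cannot be negative, and it is zero when s = 0.

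**Size (illustration only)**

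The documents state no operating characteristic to reproduce and give neither d nor s. All values of s below are assumptions, as are d = 15% and 25%. The value d = 7% borrows the Grade 3 or higher GU rate of the 29-patient salvage SBRT series in 1.2.1. That rate combines acute and late events and is not a three-week DLT rate.

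Formula: P(at most 1 of 6) = (1 − p)^6 + 6p(1 − p)^5.

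Example, d = 7%, s = 2%:
- C: p = 0.09, giving 0.568 + 0.337 = 0.905.
- A: p = 0.07/0.98 = 0.0714, giving 0.641 + 0.296 = 0.937.

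Probability that a level passes, C then A:

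| d | s = 1% | s = 2% | s = 5% |
|---|---|---|---|
| 7% | 92.3%, 93.8% | 90.5%, 93.7% | 84.4%, 93.3% |
| 15% | 75.3%, 77.3% | 72.9%, 76.9% | 65.5%, 75.8% |
| 25% | 51.0%, 52.8% | 48.7%, 52.2% | 42.0%, 50.3% |

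The gap is about 2 points at s = 1%, 3-4 points at 2% and 8-10 points at 5%.

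**Where it can still act**

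Level 3 is closed in both arms. Section 1.2.5 bases Arm 1's MTD on the late urinary criterion, which 3.1.2 does not touch. It stops Arm 2 on outside literature and disease control. As of the October 2021 amendment, three Arm 2 patients had been treated at level 1, and "three patients have been treated at dose level 2 (one is currently undergoing treatment)". The section adds: "Of all 5 patients in this arm who have completed treatment, there is no evidence of recurrence". That is 3 + 3 = 6 patients, 5 completed and 1 on treatment, so no incomplete course is reported there. What remains is any further acute DLT count and the MTD as reported, chiefly at Arm 2 level 2.

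**The case against.** The strongest reply is that the text already has a sensible reading. The delay criterion measures cumulative delay over the whole treatment, and a patient still unfinished because of toxicity more than a week past schedule fits it. Section 3.10.1 likewise treats toxicity serious enough to end therapy as a 3.1.1 event. This stands, and it confines the gap to case 3. It does not close it, because 3.1.1 never mentions a course left unfinished and 3.1.2 excludes without regard to reason.

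Second, replacing a patient who did not receive the assigned dose and had no DLT is a coherent rule, and counting a personal decision to stop over mild toxicity brings preference into the MTD. This also stands in part and is the real cost of the fix. The existing delay criterion already accepts low-grade toxicity with possible attribution.

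Third, the team would see such a stop: "Decisions about dose level enrollment and dose escalation if applicable will be made based on the toxicity data from prior patients". It would, but no rule tells it how to count the patient, and at n = 6 that should be fixed beforehand.

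Fourth, an assumed s of 5% may be high. Section 10.2 expects no drop-out, and its ceiling of 46 over 42 evaluable leaves 4/46 = 8.7% for all causes. That is fair, and it is why the table is only an illustration.

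A reader might go further and infer that toxicity stops in general are lost, or that a DLT has already been missed. The documents do not support either: 3.10.1 and the graded criteria capture most such stops, and none is reported as dropped. Nor do they show Arm 2 level 2 waiting on a six-patient test. Expansion was decided with three patients entered, on other grounds.

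**Conclusion.** The point holds in a narrow form. Followed literally, 3.1.2 can remove from the MTD count a patient whose SBRT ended because of attributable toxicity of Grade 2 or lower, or Grade 3 settling within 4 days, while a delay of more than a week from the same toxicity is a DLT. The direction is certain and depends on no assumed rate: the literal reading can only make a level look more tolerable.

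The size cannot be determined from the documents. It is zero if no such stop occurs, and the percentage-point gaps rest entirely on assumed d and s. No trial decision described in the documents is shown to have been affected. The value of the change is that the remaining acute count and the reported MTD would have a defined answer if such a stop arose. Cheap improvement.

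**What to change.** 1. In 3.1.1, insert *or failure to complete* after the word *completing* in the delay criterion, and state that the toxicity must be attributable to SBRT. Keep the exception for sexual and erectile function.
2. In 3.1.2, limit replacement to patients without a DLT who did not finish for reasons not attributable to SBRT toxicity, and record the reason for every incomplete course.

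A cross-reference in 6.3.1 and 10.3, saying that 3.1.2 sets the population for the MTD count, would remove the separate mismatch between those sections.

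The cost is a few words, one clause and one data field. It changes how patients are counted, not when treatment is stopped. The downside is that a stop for low-grade toxicity attributed only as possible becomes a DLT, so a level would be declared above the MTD somewhat more often if such stops occur.
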